## 5.2 Study drug up- and down-titration

After three days, the (adverse) effects will be evaluated by phone. In the absence of adverse events, dose will be increased to 0.01 mg/kg/day. After another three days, the effects will be evaluated again, after which the dose will be increased to 0.015 mg/kg/day. During these dosing adjustments, the maximum dose will not be allowed to exceed 0.5 mg twice daily. In case of reported adverse events during any of the dose evaluations, the daily dose will be halved. Then, after three days without adverse events, the dose will be increased to the dose that was prescribed at the time adverse events appeared. When adverse events re-appear, subjects will continue at the lowest tolerable dose.

At the end of the study period, starting in the evening of Day 22, clonazepam will be tapered by decreasing the daily dose by 0.01 mg/kg/day every three days.

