## Part B

- Active medication. Clonazepam (Rivotril) droplets for oral use, solution 2.5 mg/ml, dissolved in lemonade, tea or juice.
- Placebo: dissolved in lemonade, tea or juice

Study drug or placebo during part B will be administered to the subjects as follows:

- Day 1-3: Starting dose is 0.005 mg/kg, twice daily (max 0.5 mg, twice daily)
- Day 4-6: 0.01 mg/kg, twice daily (max 0.5 mg, twice daily)
- Day 7-22: 0.015 mg/kg, twice daily (max 0.5 mg, twice daily)

Patients will receive a single starting dose at their first visit of 0.005 mg/kg (max 0.5 mg). Patients will be monitored for 5 hours for safety, PK, and biomarker effect. If the dose on day 1 is well tolerated, patients will take the same dose before bedtime, and continue this regimen as described.

After three days, the (adverse) effects will be evaluated by phone. If the dose on day 1 is well tolerated, the dose will be increased to 0.01 mg/kg/day. After another three days, the effects will be evaluated again, after which the dose will be increased to 0.015 mg/kg/day. During these dosing adjustments, the maximum dose will not exceed 0.5 mg, twice daily. In case of relevant adverse events during any of the dose evaluations, the daily dose will be halved. Then, after three days without relevant adverse events, the dose will be increased to the dose that was prescribed at the time adverse events appeared. When relevant adverse events re-appear, subjects will continue at the lowest tolerable dose.

At the end of the study period, clonazepam will be tapered by decreasing the daily dose by 0.01 mg/kg/day every three days.

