#### 1.4 Study rationale

#### 1.4.1 Benefit and risk assessment

This is an interventional trial with the aim of benefiting patients. The NeuroCart® assessments have been previously evaluated in the study population (study CHDR1828). The measurements were well tolerated, and most patients indicated they would consider participating again in a trial when asked. The most disliked assessment (EEG measurements) are not included in this trial. Therefore, we estimate the assessment burden for subjects is relatively lower than during CHDR1828.

The actual burden for subjects consists of the time spend at CHDR and the potential side-effects from clonazepam treatment. The 4 study days will last approximately 6.5 hours, but include 5 hours of break time. In this time, subjects can roam freely and sufficient entertainment will be arranged together with parents. The study does not include blood draws or other invasive measurements. Clonazepam is a registered drug and approved for use in pediatric patients. Possible adverse events include fatigue, diminished concentration, dizziness and headache. Furthermore, extremely rare paradoxal reactions have been reported: irritability, aggression, agitation, nervousness, hostility, anxiety, sleep disturbances, nightmares, abnormal dreams, hallucinations. Patients will be monitored during each study day and the investigator will be continuously available for parents and caregivers. Dose-adjustment or study discontinuation will follow in the case of clinically relevant adverse events.

Study subjects will have potential benefit from study participation. Pre-clinical data suggests an effect on behavior and cognition. The additional value of this research is in gaining the first insights into the neurocognitive effects of clonazepam treatment on ARID1B-related ID subjects and possible validation of novel noninvasive endpoints obtained via the NeuroCart®. The proposed research can be considered group-related because it is only feasible by including ARID1B-related ID patients themselves.

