# 1.4.6 Safety margin calculations, dose selection, dose escalation, and stopping criteria

The optimal dose of clonazepam to restore the excitation/inhibition imbalance is not known. The dose used pre-clinically (0.0625 mg/kg) [11] is comparable to the doses used in mouse seizures models (0.08-0.5 mg/kg). The HED is 0.0625 mg/kg \* scaling factor 0.08 = 0.005 mg/kg, thus 0.35 mg for an adult male, in the same order as the regular starting dose (0.5 mg twice daily), but much lower than the regular maintenance dose (4-8 mg/day). Although generally considered safe, paradoxical reactions have been described in children and elderly. Usually these occur at higher doses. Other reported side effects include dizziness and drowsiness, which are also dose-related. Tolerance usually develops in 1-2 weeks [22, 23].

The dose used in this study is based on the following rationale:

- 1. The pre-clinically effective dose is similar to the starting dose in preclinical seizure models, and the human equivalent dose is in the range of the recommended starting dose for seizures in humans.
- 2. The dose is identical to the dose given to the case of the 12 year old ARID1B patient currently on clonazepam with good clinical effect and absence of toxicity.
- 3. Clonazepam is a registered drug. The recommended starting dose is the same as given in this study.

Therefore, the patients will receive a single starting dose at their first visit of 0.005 mg/kg (max 0.5 mg). Patients will be monitored for 5 hours for safety, PK, and biomarker effect. If the dose on day 1 is well tolerated, patients will take the same dose before bedtime, and continue this regimen as described.

After three days, the (adverse) effects will be evaluated by phone. If the dose on day 1 is well tolerated, the dose will be increased to 0.01 mg/kg/day. After another three days, the effects will be evaluated again, after which the dose will be increased to 0.015 mg/kg/day. During these dosing adjustments, the maximum dose will not exceed 0.5 mg, twice daily. In case of relevant adverse events during any of the dose evaluations, the daily dose will be halved. Then, after three days without relevant adverse events, the dose will be increased to the dose that was prescribed at the time adverse events appeared. When relevant adverse events re-appear, subjects will continue at the lowest tolerable dose.

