## 8 SAFETY REPORTING

## 8.1 Definitions of adverse events

An Adverse Event (AE) is any untoward medical occurrence in a subject who is participating in a clinical study performed. The AE does not necessarily have to follow the administration of a study drug, or to have a causal relationship with the study drug. An AE can therefore be any unfavourable and unintended sign (including an abnormal laboratory or vital sign finding), symptom, or disease temporally associated with the study participation, whether or not it is related to the study drug.

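### Section 5.2 halves the Part B dose for any reported adverse event, whereas the synopsis, 1.4.1 and 1.4.6 tie dose changes to relevant events

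*Protocol*

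**What the plan says.** The Part B titration rule is written out in full in three places: the synopsis (Investigational drug, Part B), section 1.4.6 and section 5.2. In each, effects are evaluated by phone after three days and again three days later. Table 2, footnote 7, gives the Day 3 and Day 6 calls to the study physician.

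Section 5.2 carries no qualifier at any step. For the first increase: "In the absence of adverse events, dose will be increased to 0.01 mg/kg/day". For reduction: "In case of reported adverse events during any of the dose evaluations, the daily dose will be halved". The previous dose returns after three days free of adverse events, and the rule ends: "When adverse events re-appear, subjects will continue at the lowest tolerable dose".

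Section 1.4.6, which the synopsis repeats, sets a different test. For the first increase: "If the dose on day 1 is well tolerated, the dose will be increased to 0.01 mg/kg/day". For reduction: "In case of relevant adverse events during any of the dose evaluations, the daily dose will be halved". Restoration requires three days free of relevant events, and the closing sentence, as given in the synopsis, is "When relevant adverse events re-appear, subjects will continue at the lowest tolerable dose". Section 1.4.1 agrees in substance: "Dose-adjustment or study discontinuation will follow in the case of clinically relevant adverse events".

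None of these places defines 'relevant'. Section 8.1 does define an adverse event, and broadly: it covers unfavourable signs, symptoms and diseases "temporally associated with the study participation, whether or not it is related to the study drug".

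**The concern.** The two triggers are not synonyms. Given the definition in 8.1, a cold or a bruise mentioned on the phone is an adverse event. Under 5.2 it stops the increase and cuts the dose; under 1.4.6 it does neither if the physician considers the dose well tolerated. Section 5.2 is the section headed for up- and down-titration, so it is where staff would look. Section 5.4 makes the investigator responsible for dosing in line with the protocol, yet for such a report any choice departs from one section or another.

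What is at stake is dosing below the schedule without clinical need, and dosing that depends on which section was read. Section 1.4.1 lists fatigue, diminished concentration, dizziness and headache as possible events. Section 1.4.7 chose three weeks of treatment so that effects could be seen once tolerance to sedation has developed. A rule that reduces the dose for every early mild report works against that aim. The multiple-dose objective rests on ABC and CGI-I at Day 22, and NeuroCart is also measured that day.

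**Working it through.** The protocol states no figure for this point, so nothing has to be reproduced. The check is a comparison of the texts, followed by dose arithmetic to size one case.

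**Texts side by side**

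| Step | Section 5.2 | Synopsis and 1.4.6 |
|---|---|---|
| First increase | no adverse events | Day 1 dose well tolerated |
| Halving, at any evaluation | any reported event | relevant events |
| Restoration after three days | free of any event | free of relevant events |
| End state | any event re-appears | relevant events re-appear |

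In 5.2 the explicit no-event condition is attached to the first increase only. The second increase is blocked through the halving rule, which covers every evaluation. The conflict is therefore present at both calls.

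**Inputs (section 5.1, Part B, mg per intake, twice daily)**

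- Start dose: min(0.005 × weight, 0.5).
- Second step, Days 4-6: min(0.010 × weight, 0.5). The cap binds at 0.5/0.010 = 50 kg.
- Halved start dose: start/2. The cap on the start dose binds at 0.5/0.005 = 100 kg.

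**Case:** a minor, non-relevant event is reported at the Day 3 call, and the physician judges the dose well tolerated. The ratio on Days 4-6 is the second step (1.4.6) divided by half the start dose (5.2).

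| Weight | 1.4.6 | 5.2 | Ratio |
|---|---|---|---|
| 40 kg | 0.010 × 40 = 0.40 mg | 0.005 × 40 / 2 = 0.10 mg | 4 |
| 50 kg | 0.50 mg | 0.005 × 50 / 2 = 0.125 mg | 4 |
| 70 kg | 0.50 mg (cap) | 0.005 × 70 / 2 = 0.175 mg | 2.9 |
| 100 kg | 0.50 mg (cap) | 0.50 / 2 = 0.25 mg | 2 |

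Up to 50 kg the ratio is 0.010/0.0025 = 4 at every weight. From 100 kg it is 2.

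The titration sentences give the steps in mg/kg/day, while 5.1 gives mg/kg twice daily. Read per day, the start dose is 2 × 0.005 = 0.01 mg/kg/day, its half is 0.005, and the next step is 0.01, so the ratio is 0.01/0.005 = 2. That unit conflict is a separate matter; the instructions differ under either reading.

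**How long it lasts.** Under 5.2 the halved dose covers Days 4-6 and the start dose can return on Day 7. If there is no recurrence and escalation resumes in three-day steps, the second step covers Days 10-12 and the top step starts on Day 13, well before Day 22. Resumption is an assumption: each version restores the dose held when events appeared and says nothing about going further. If any event re-appears, 5.2 fixes the patient at the lowest tolerable dose, and no later step lifts it before Day 22.

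**The case against.** The strongest reply is that a physician makes the calls, that 5.2 itself speaks of evaluating effects, and that words such as tolerable suggest drug effects are meant. Few physicians would halve a dose for a bruise. That is a fair account of likely practice, but it means the physician would be following 1.4.6 rather than 5.2 as written. The stopping criteria in 1.4.6 and the discretion in 4.6.1 concern stopping or interrupting the drug; they do not settle when to halve. It is also fair that 1.4.1 says adjustment follows clinically relevant events without saying that nothing else may trigger it. The direct conflict is with 1.4.6 and the synopsis, and 1.4.1 supports their reading.

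A second reply is that the consequences are limited. The study is exploratory with no primary endpoint (1.4.8), exposure is described from diary records (9.7.3), and the modelling relates exposure to effect (9.9.4). This stands and keeps the point minor, though recording a wrong dose does not correct it.

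A reader might also infer that *lowest tolerable dose*, common to all three versions, is an error that must become the highest dose tolerated. The documents do not support that. The only lower dose the rule names is the halved one, and a cautious end state may be intended. The highest tolerated dose could be a step held for only three days. With the 20-40 hour half-life in the synopsis, 72 hours reaches 1 − 2^(−72/40) = 71% to 1 − 2^(−72/20) = 92% of steady state. At 40 kg, after recurrence at 0.50 mg, that wording would select 0.40 mg where halving gives 0.25 mg. What stands is that the phrase is ambiguous.

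**Conclusion.** The contradiction is real and lies in the current text. The same Day 3 report leads to half the start dose under 5.2 and to the next step under 1.4.6: in the twice-daily units of 5.1, a fourfold difference on Days 4-6 up to 50 kg, falling to twofold from 100 kg. This assumes an event that the physician judges not relevant, on a dose otherwise well tolerated.

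A reader might go further and compute Day 22 doses at 17% (20 kg: 0.05/0.30 mg) to 50% (100 kg: 0.25/0.50 mg) of schedule. Those figures need an event at the call, halving, restoration, recurrence on the restored start dose, and the halved dose then held to the end. The protocol gives no rate for any of these steps, nor a weight distribution, so the figures do not measure an effect on the trial and the number of patients affected cannot be estimated.

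Nor does the conflict by itself imply bias. The rule is applied blind and in both periods; halving placebo changes nothing pharmacologically, while halving clonazepam lowers exposure. If the effect grows with dose, the likely result is dilution of the treatment contrast. Overall this is a minor internal contradiction in a dosing rule, worth correcting because followed literally it under-doses patients without clinical need.

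**What to change.** In section 5.2, insert 'relevant' before 'adverse events' in the escalation, halving, restoration and re-appearance sentences, replacing 'reported' in the halving sentence. State that relevance is judged by the blinded study physician who makes the calls. Do not add a condition that the event be related to study drug: no current section has one, and it would narrow a safety rule, for example for an intercurrent respiratory illness in a child taking a benzodiazepine.

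In the same amendment, say in the synopsis, 1.4.6 and 5.2 what the lowest tolerable dose means, for instance whether it is the halved dose. This is a secondary wording point.

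The cost is wording only, with no new visits, assessments or analyses. Because the change alters a dosing instruction, it would probably count as substantial under 10.6.1, needing ethics committee approval and no objection from the competent authority. Amendment 3 classed its change to the escalation decision as substantial and also changed the ICD.

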## 5.3 Study drug packaging and labelling

Study drug will be ordered at the pharmacy of Leiden University Medical Center. Upon arrival at the pharmacy, the investigational products should check them for damage and verify proper identity, quantity, integrity of seals and temperature conditions, and report any deviations or product complaints upon discovery. The dispensing of the study drug will be performed by the pharmacy. Study drug will be dispensed for each subject according to the randomization list. Study drug packaging will be overseen by the Leiden University Medical Centre Pharmacy and bearing a label with the identification required by local law, the protocol number, drug identification, and dosage.

## 5.4 Drug accountability

Drug accountability will be maintained by the Leiden University Medical Centre Pharmacy and assessed by maintaining adequate study drug dispensing records. The investigator is responsible for ensuring that dosing is administered in compliance with the protocol. Delegation of this task must be clearly documented and approved by the investigator. All in-house study drug administration will occur under medical supervision.

## 5.5 Treatment assignment and blinding

#### 5.5.1 Randomization and treatment assignment

Subjects must be randomized in a consecutive order starting with the lowest number.

Subject numbers consist of 3 digits. Subject numbers for part A will consist of 101-120 and subject numbers for part B of 201-220. Stratification for gender takes place in Promasys, by adding key value "F" to subject numbers for females and "M" to subject numbers for males. There will be no reserve subjects. The randomization code will be generated by a study-independent CHDR statistician. The randomization code will be unblinded/broken and made available for data analysis only after study closure, i.e., when the study has been completed, the protocol deviations determined, and the clinical database declared complete, accurate and locked. The randomization code will be kept strictly confidential. Sealed individual randomization codes, per subject and per treatment, will be placed in a sealed envelope containing the labelled 'emergency decoding envelopes' will be kept in a safe cabinet at CHDR.

#### 5.5.2 Blinding

This study will be performed in a double-blind fashion. The investigator, study staff, subjects, and monitor will remain blinded to the treatment until study closure. The investigational drug and its matching placebo are indistinguishable and will be packaged in the same way.

The investigator will receive a set of sealed emergency codes to be broken in case of emergency situations. If the identity of the study drug administered needs to be known in order to manage the subject's condition i.e., in case of a medical emergency or in the case a SUSAR occurs, the treatment emergency code for that subject may be broken and the study drug identified. All such occurrences should be documented in the study file. Treatment emergency codes should not be broken except in emergency situations and, if possible, the investigator should be contacted before the emergency code is opened. Just prior to database lock, the unused emergency code labels will be checked and a statement to the effect that all are intact (or not as the case may be) will be made on the database lock form.

#### 6 STUDY ENDPOINTS

#### 6.1 Safety and tolerability endpoints

- Treatment-emergent (serious) adverse events ((S)AEs).
- Concomitant medication

## 6.2 Pharmacokinetic endpoints

Part A: serum and saliva. Part B: saliva only.

- The maximum serum concentration, Cmax
- $\circ$   $\;$  The time to reach maximum serum concentration, tmax  $\;$
- $\circ~$  The terminal disposition rate constant (\lambdaz) with the respective half-life, t1/2  $\,$
- The area under the serum concentration-time curve from zero to infinity, AUC0-inf
- The area under the serum concentration-time curve from zero to t of the last measured concentration above the limit of quantification, AUC0-last
- o Clearance, Cl
- Volume of distribution, Vz

#### 6.3 Pharmacodynamic endpoints Questionnaire endpoints

- ABC questionnaire (parents, teacher)
  - o Irritability subscale
  - Social Withdrawal subscale
  - Stereotypic Behavior subscale
  - Hyperactive/Noncompliance subscale
  - Inappropriate Speech subscale
- Clinician's Global Impression (CGI-I and CGI-S)
  - Score at the start (CGE-S) and at the end (CGE-I)of the treatment period.

#### NeuroCart endpoints

- Saccadic eye movements:
  - o saccadic reaction time (second),
  - o saccadic peak velocity (degrees/second), and
  - saccadic inaccuracy (%);
- Smooth pursuit eye movements:
  - o percentage of time the eyes of the subjects are in smooth pursuit of the target (%);
- Body sway:
  - antero-posterior sway (mm);
- Adaptive tracking:
  - average performance (%);
- Animal fluency:
  - Number of correctly named animals in one minute;
- Finger tapping
  - o Amount of taps in 10 seconds;
- Trial@home endpoints
- Steel HR watch
  - Physical activity
  - Sleep (duration, %light sleep, amount of times woken up)
  - Heart rate
- Adapted NeuroCart endpoints for home use:
  - Tapping frequency
  - Adaptive tracking average performance
  - o Animal fluency

## 7 STUDY ASSESSMENTS

See Table 1 and 2 for the time points of the assessments.

## 7.1 Safety and tolerability assessments

The definitions, reporting and follow-up of AEs, SAEs and potential pregnancies are described in section 8.

## 7.1.1 Vital signs

Evaluations of systolic and diastolic blood pressure, pulse rate, respiratory rate, and temperature will be performed throughout the study. Pulse and blood pressure will be taken after 5 minutes in the supine position. Automated oscillometric blood pressures and pulse rate will be measured using a Dash 3000, Dash 4000, Dynamap 400 or Dynamap ProCare 400.

## 7.1.2 Weight and height

Weight (kg) will be recorded at screening (part A) or the first visit (part B). Height (cm) will be recorded and body mass index (BMI) calculated.

## 7.1.3 Physical examination

Physical examination (i.e., inspection, percussion, palpation and auscultation) will be performed on indication during the course of the study. Clinically relevant findings that are present prior to study drug initiation must be recorded with the subject's Medical History. Clinically relevant findings found after study drug initiation and meeting the definition of an AE (new AE or worsening of previously existing condition) must be recorded.

## 7.2 Baseline variables

The following baseline variables will be recorded: age, gender, diagnosis, specific ARID1B mutation, clinical phenotype, IQ (if available), dyslexia.

## 7.3 Questionnaire assessments

The Dutch translation of the Aberrant Behaviour Checklist (ABC) will be used [24]. The ABC is a validated questionnaire used for patients with intellectual disability. It consists of 58 symptoms of which the severity of symptoms during the last 2 weeks is scored by parents on a scale of 0-3 (0 = no problem, 3 = the problem is very severe). Parents of ARID1B subjects will complete the questionnaire on day 1 and day 22 of the two treatment periods. Teachers or primary caregivers (in the case of institutionalized care) will complete the questionnaire at the earliest opportunity after day 1 and day 22.

The Clinician Global Impression Score (CGI) is a well-validated clinician-rated measure commonly used in drug studies because it allows the clinician to integrate all sources of information, including the parent/caregiver history, observations in the clinic, and reports from other sources, into a single rating of severity (CGI-S) and improvement (CGI-I) during treatment. The CGI-S will be assessed on day 1 of every treatment period.

For this assessment, the investigator considers all aspects of the subject's neurobehavioral function, including but not limited to internalizing problems, externalizing problems, and social engagement, and rates a scale employing a 7-point Likert scale. The CGI-I monitors improvement and is scored on a 7-point Likert scale: very much improved, much improved, minimally improved, no change, minimally worse, much worse, very much worse. The score will be determined via a semi-structured interview with parents on day 22 of both treatment periods. Furthermore, an additional score will be

determined via a semi-structured phone interview with teachers or primary caregivers at the earliest opportunity after day 22 of both treatment periods.

Conversations made for the CGI assessment will be recorded for review by an independent physician.

